5.2 Recruitment Methods

Step 1 (determine potential eligibility based on existing administrative data): The study will begin with a 12-month retrospective baseline period in which Veteran clinical eligibility (i.e., diagnosis of CVD or CVD-risk) will be determined using data from CDW. We will not exclude any Veterans based on race, gender, or other classes (e.g., handicapped). We will exclude two classes of Veterans: 1) those with impaired decision-making and 2) those who are illiterate or have limited or no English proficiency. This initial step involves secondary data analysis only; we will not recruit Veterans as subjects for use of secondary data; we will request a HIPAA Waiver of Authorization for this step.

Step 2 (initial outreach by mail to potentially eligible participants): For the next 12 months and on a weekly basis, the study Data Analyst will produce a primary care appointment list of eligible Veterans at each study site using data from CDW. In advance of an eligible Veteran's appointment, the research team will mail the Veteran the following documents:

- A Cover Letter briefly describing the study and inviting participation (see **Appendix C**);
- A Study Fact Sheet detailing the elements of informed consent and describing the study in more detail including that participants will complete a brief survey and based on the survey results, those deemed eligible for the RCT will be randomized to one of three study arms, while those deemed not eligible, will be done with the study after completing the initial survey (see **Appendix D**);
- A post card that includes phone numbers for the Veteran's VA Medical Center, VA Veterans Crisis Line, and National Call Center for Homeless Veterans (see **Appendix E**);
- An opt-out postcard (postage included) that will explain that the Veteran is eligible for the initial phase of the study and may be eligible for the subsequent phase, an RCT; indicate that if they are interested in

potentially participating that an RA will contact them by phone in advance of the Veterans upcoming PCP appointment, and; if they are not interested to return the opt-out card within 3 days of receiving it (see **Appendix F**).

Step 3 (phone follow-up to recruit, consent, and screen for eligibility): The research team will provide the final list of site-specific eligible Veterans who did not return an opt-out card to the RA situated at each study site. Guided by a phone script (see **Appendix G**), the RA will contact these Veterans by phone up to three weeks following the opt-out card mailing (making up to 5 attempts if they cannot reach the Veteran) to: 1) describe the study, 2) request participation, including potential randomization to one of three study arms if deemed eligible following the initial index screen, participation in subsequent surveys, and possible contact by phone to invite participation in a qualitative interview; and 3) obtain verbal consent. The RA will review the elements of informed consent and answer any questions the potential respondent might have. Among Veterans who verbally consent to participate, the RA will administer the index unmet need screen and, if Veteran is eligible for the RCT (i.e., 1 or more unmet needs) randomize them to one of the three trial arms using the sealed opaque envelope program (see **Appendix A** for details).

Step 4 (recruitment for qualitative interviews; Veterans): Among study participants, we will purposefully sample 60 Veterans to participate in qualitative interviews. Sample selection and recruitment will be conducted on a rolling basis after the 6-month unmet needs re-screen is completed. The study RA will phone selected Veterans, ask for participation in an interview, and among those who accept, schedule an interview time. Note: As part of the RCT informed consent process, participants will be told that they may be contacted by phone to participate in a qualitative interview, which we believe eliminates the need to mail opt-out cards prior to contacting Veterans by phone for this phase of the study. During this initial call we will not re-consent participants but will review and remind potential participants of the purpose of the interviews and the elements of informed consent.

Step 5 (recruitment for qualitative interviews; Agency representatives): We will also seek a purposeful sample of representatives of the VA and community programs that Veterans are referred to as a result of the intervention. Potential interviewees will first be contacted by email or phone (dependent on contact information available in VA Outlook and community agency websites) to assess their interest in being interviewed for the project. Each potential interviewee will be emailed a letter of invitation from the site PI (see **Appendix H** for Resource Representative Recruitment Email). The letter will contain all the elements of

consent: the risks and benefits of the study, confidentiality procedures, study personnel to contact regarding questions and concerns (including contact numbers for the VA Central Institutional Review Board), that participation is voluntary, and that participating or not participating in the interview will not affect their VA appointment (in the case of VA program representatives) or their organizational relationship with the VA (in the case of community program representatives). If a potential interviewee expresses interest in participating, we will use both email and phone to schedule an interview with the participant. A member of the study team will then review the letter before conducting an interview with any potential interviewee. Participation in the interview will be an indication of consent.

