5.6 Data Analysis

Study Sample and Power Analysis

We aim for a total of 880 Veterans enrolled in the RCT (293/arm) based on power analyses provided below. Based on the study team's prior primary care-based studies with a similar recruitment approach, we anticipate 80% of patients approached to complete the index screen will participate. Based on pilot data from the Bedford MA VA where 78% of Veterans reported one or more needs, we then conservatively estimate that 50% of Veterans screened will report at least one of the nine unmet needs for which we will screen.

Thus, to yield a final sample of 880 Veterans with at least one unmet need enrolled in the study, we anticipate needing to approach 2200 eligible Veterans (733/site, or ~3 patients/day/site) i.e., of 2200, 80% (1760) will agree to participate in the study and of these, 50% (880) will have one or more unmet needs and be eligible for the RCT. If the participation rate or proportion of Veterans reporting at least one unmet need is lower than expected, we will increase the number of Veterans that we approach. We reviewed VA administrative data to determine the anticipated weekly count of Veterans eligible per site to participate in the study and there are more

than enough eligible Veterans to approach for additional screening if needed. We also anticipate drop-out rates at the 8-week follow-up survey to assess connection to resources and the 6-month unmet needs re-screen, respectively. Though the study team's prior study achieved a 65% follow up participation rate, here we conservatively anticipate a 50% participation rate for both the 8-week follow-up survey and the 6-month re-screen, reducing the sample for the three arms first to 440 Veterans total and then to 220 Veterans total.

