Statistical Power for Aim 1: With a sample of N=1760 Veterans completing the index unmet needs screening, we will have 80% power to detect small effect sizes ($f^2=.01$; $OR=1.47$) using 2-tailed significance tests at the $\alpha=.001$ level if the intraclass correlation coefficient (ICC) (for the nesting of patients within sites) is negligible, or medium effect sizes ($f^2=.15$; $OR=4.07$) even if the ICC is as high as .02 for testing associations between the presence of each unmet need and sociodemographic, adherence, utilization, and clinical (BP only) variables. HbA1c is anticipated to be a relevant clinical outcome for only 40% of the sample; for HbA1c, we will have 80% power to detect small effect sizes ($f^2=.03$; $OR=1.84$) using 2-tailed significance tests at the $\alpha=.001$ level if the ICC is negligible.

Statistical Power for Aim 2: The power analysis for Aim 2 focused on the primary outcome of connection to resources to address unmet needs. The sample size was determined based on previous research outside VA which found that individuals who completed a screening and referral intervention were 15% more likely (adjusted Odds Ratio (aOR)=2.1) to have enrolled in a new community resource to address unmet needs post-referral compared to patients in the non-intervention arm. In the present study, we will have 80% power to detect an effect of this size (aOR=2.1) across the three arms using 2-tailed significance tests at the $\alpha=.05$ level, even if we assume an attrition rate as high as 50% for the follow-up phone call at 8-weeks post-screen (retained N=440 across all sites and arms) and a conservative ICC value for patients nested within sites of .01. Previous empirical work found ICC values <.0001 when adjusting for a small number of covariates (e.g., race, marital status) to examine new connections to resources to address unmet needs; we intend to collect and use these covariates in the present study as well. Assuming an ICC value of .0001, we will have 80% power to detect an effect as small as an aOR=1.7 if we assume a 50% attrition rate for the 8-week follow-up phone call, or as small as an aOR=2.0 if we assume a 70% attrition rate. We based our attrition rate upon the study team's prior study where Veterans

had low incomes, high unemployment and low educational status, yet only 35% were lost to a follow-up interview.

Quantitative Data Analysis

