Examining marginal intervention effects over and above S&R occurring as part of usual care. Finally, given that Veterans may already be accessing resources for some unmet needs as part of usual care and related to existing screening for homelessness and food insecurity, we will conduct supplemental analyses to examine whether our intervention effects hold when controlling for use of VA SW services not attributable to the present intervention (e.g., services already being accessed separate from the study intervention). Although we will specifically be assessing connection to new resources following the S&R mechanisms in our three study arms, it is possible that individuals already connected to certain resources will be more likely to seek out additional support/resources (e.g., because they already have successful experiences using VA resources to meet certain unmet needs) or less likely to seek out additional support/resources (e.g., because they feel they already have the support they most need). Because VA screens for housing and food insecurity, Veterans may already be accessing resources for these. To examine whether the intervention has a significant impact on connection to new resources, unmet need reduction, and more distal health outcomes when controlling for use of VA SW services not attributable to the present study, we will conduct supplemental analyses that control for connection to resources associated with each of our nine unmet needs prior to enrollment in our intervention. Use of SW resources not attributable to our study will be measured via CPRS encounter forms, where SWs record encounters with patients, and from referral/consult documentation available in CPRS during the 12 months prior to the start of our intervention.

Qualitative Data Analysis

Aim 3: Identify barriers and facilitators to Veterans' connecting with resources to address unmet needs and getting needs met, and explore potential explanatory factors related to the relative success of each study arm.

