i. Within the past 6 months, you worried that your food would run out before you got money to buy more.

- Often true
- Sometimes true

- Never true

ii. Within the past 6 months, the food you bought just didn't last and you didn't have money to get more.

- Often true
- Sometimes true
- Never true

10a. (If Often/Sometimes true to 10i or 10ii): Are you already receiving assistance with your food needs?

10b. (If Yes to 10a): Would you like additional assistance?

10c. (If No to 10a): Would you like assistance with your food needs?

LEGAL AND TRANSPORTATION

11. Are you currently dealing with any legal issues, for which you may need assistance?

- Yes
- No

11a. (If Yes): Are you already receiving assistance with your legal needs?

11b. (If Yes to 11a): Would you like additional assistance?

11c. (If No to 11a): Would you like assistance with your legal needs?

12. In the past 6 months, has lack of transportation kept you from medical appointments, meetings, work, or getting things needed for daily living: *Check all that apply*

- Yes, it has kept me from medical appointments or from getting my medications
- Yes, it has kept me from non-medical meetings, appointments, or getting the things that I need
- No

12a. (If Yes): Are you already receiving assistance with your transportation needs?

12b. (If Yes to 12a): Would you like additional assistance?

12c. (If No to 12a): Would you like assistance with your transportation needs?

SOCIAL AND EMOTIONAL STATUS

13. In the last 6 months, how often did you feel lonely or isolated?

- Never
- Rarely
- Sometimes
- Often

- Always

13a. (If Sometimes/Often/Always): Are you already receiving assistance with your feelings of loneliness or isolation?

13b. (If Yes to 13a): Would you like additional assistance?

13c. (If No to 13a): Would you like assistance with your feelings of loneliness or isolation?

14. Stress is when someone feels tense, nervous, anxious, or can't sleep at night because their mind is troubled. In the last 6 months, how often did you feel stressed?

- Not at all
- A little bit
- Somewhat
- Quite a bit
- Very much

14a. (If Somewhat/Quite a bit/Very much): Are you already receiving assistance with your feelings of stress?

14b. (If Yes to 14a): Would you like additional assistance?

14c. (If No to 14a): Would you like assistance with your feelings of stress?

EXPOSURE TO VIOLENCE

15. Is anyone in your life hurting or threatening you?

- Yes
- No

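### No stated analysis uses the index-screen answers on existing help and wish for help; pre-specify them as a baseline covariate and effect modifier

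*Combined protocol and SAP*

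**What the plan says.** **Entry.** Section 5.2, Step 3: "if Veteran is eligible for the RCT (i.e., 1 or more unmet needs) randomize them to one of the three trial arms". Appendix A and the remaining part of the phone script (Appendix G, item 8) give the same rule. None of them adds a condition on wanting help.

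**What is collected before randomisation.** For most domains Appendix I follows an identified need with an item on existing assistance (the a items) and an item on wanting assistance or more of it (the b and c items). For stress, the last of these is "14c. (If No to 14a): Would you like assistance with your feelings of stress". Employment has the single item 9a. Section 5.5 drops the preference items from the 6-month survey, so they exist at index only.

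**What the analyses use.** The primary Aim 2 model in 5.6 compares connection to new resources at 8 weeks across arms, with patients nested in sites, and lists no covariates. The power text refers to earlier work "adjusting for a small number of covariates (e.g., race, marital status) to examine new connections to resources to address unmet needs" and intends to use those covariates here. The paragraph on differences in intervention effectiveness takes type and number of needs as modifiers. The paragraph on marginal effects over usual care plans supplemental control for prior connection for each of the nine needs, and says of its data: "Use of SW resources not attributable to our study will be measured via CPRS encounter forms", together with referral and consult records for the prior 12 months.

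**The concern.** The 8-week question (Appendix J, item 1) asks about new programs for the needs identified at index. A Veteran who is already helped and wants no more has less reason to answer yes, whatever the arm. The plan accepts part of this reasoning: in the usual-care paragraph of 5.6 it says that Veterans already connected may seek less, or more, additional support.

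The index answers are the only measure of this that is taken before randomisation and in every arm. Refusal of the social worker is seen only after randomisation and only in the Assistance arm. CPRS records VA social work, so it may miss community help, and it is not a record of whether help was wanted.

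Two things are at stake. One is a modest amount of power. The other is interpretation: sections 2.0 and 5.6 say the trial should show for which Veterans a lighter intervention is enough. The wish for help is an obvious candidate for that split, and a split chosen after arm results are known is post hoc.

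**Working it through.** **1. Inputs from the documents.** Two-sided alpha .05; 880 enrolled in three arms; 440 retained at 8 weeks, so n = 440/3 = 146.7 per arm. Target: "we will have 80% power to detect an effect of this size (aOR=2.1) across the three arms using 2-tailed significance tests". The source effect is that patients "were 15% more likely (adjusted Odds Ratio (aOR)=2.1) to have enrolled in a new community resource". No control rate is stated.

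**2. Implied control rate.** Read the 15% as percentage points and solve p2 = 2.1·p1/(1 − p1 + 2.1·p1) with p2 − p1 = 0.15. The lower solution is p1 = 0.2146, p2 = 0.3646 (the upper is 63.5% v 78.5%).

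**3. Reproducing the plan's 80%.** Two arms, with p̄ = 0.2896:

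z = [(p2 − p1)√n − 1.96·√(2p̄(1 − p̄))] / √(p1(1 − p1) + p2(1 − p2)) = (1.817 − 1.257)/0.633 = 0.884

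Power is 81.2%, which agrees with the stated 80%. This is pairwise and takes no inflation for clustering; whether that is right is a separate matter.

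**4. What a group wanting no help would do (assumed, not documented).** Let a share q want no help and connect at rate c0 in both arms, and let OR 2.1 hold in the rest. Each arm's rate is (1 − q)·p + q·c0. With q = 20% and c0 = 5%:

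- Screening: 0.8 × 0.2146 + 0.2 × 0.05 = 0.1817
- Assistance: 0.8 × 0.3646 + 0.2 × 0.05 = 0.3017
- Overall OR: (0.3017/0.6983)/(0.1817/0.8183) = 1.95
- Power from the formula in step 3: 67%

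Over c0 from 2% to 10%, at a 21.5% control rate among those wanting help:

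| q | overall OR | unadjusted power |
|---|---|---|
| 10% | 2.00-2.03 | 74-75% |
| 20% | 1.91-1.97 | 66-68% |
| 30% | 1.82-1.91 | 57-60% |
| 50% | 1.62-1.79 | 37-43% |

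**5. What adjustment returns.** Simulation with 147 per arm, all randomised Veterans kept, comparing a crude score test with a Mantel-Haenszel test stratified by wish for help. At a 21.5% control rate and c0 = 5%:

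| q | crude | stratified |
|---|---|---|
| 20% | 67.7% | 69.8% |
| 30% | 59.8% | 62.8% |
| 50% | 40.0% | 43.2% |

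For q of 20-50% and c0 of 5-10%, the gain is about 1.5-4 points at a 21.5% control rate and about 2.5-11 points at 30-40%. The largest gain comes at 40% control, c0 = 5% and q = 50% (about 43% to 53%). The highest adjusted power anywhere in that grid is about 79%.

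**6. For comparison.** Analysing only those wanting help within the 880 gives 71.9% (q = 20%) or 66.1% (q = 30%) at a 21.5% control rate. Enrolling 880 who all want help would return 81.2%, but at q = 20% completed screens would rise from 1760 to 880/(0.5 × 0.8) = 2200.

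**7. Can the indicator be derived as the form stands?** Not cleanly.

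- Item 7a is asked after Yes to Q6 or Q7, but Yes to Q6 means stably housed. A Veteran answering No to both is never asked, while one who is stably housed and unworried is.
- Item 15a depends on frequency answers, while Q15 offers only Yes and No.
- Employment has 9a and no separate item on additional help. In 9a and in the legal question (Q11), wanting or needing help is already part of the screening question.

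**The case against.** **Broad entry is deliberate.** The trial tests systematic screening and referral for possible wider adoption. For that question, the effect that includes Veterans who decline help is the target, not a diluted version of it. This stands. A reader might infer that the entry rule is an error or biases the result; the documents do not support that, and the source OR of 2.1 may already include such people.

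**Prior help is already handled.** A reader might infer that the plan ignores it. It does not: 5.6 plans supplemental control for prior connection need by need, and nothing there rules out the index answers. What remains is that CPRS is the only source named, and that the wish for help is not covered.

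**The predictor and the dilution are assumed.** This also stands. No share, rate or association is given, and the plan leaves the direction open for Veterans already connected. No effect in those wanting no help is a further assumption: the Assistance script encourages decliners to reconsider, and the social worker uses motivational interviewing. The answers are a plausible predictor, not a demonstrated strong one.

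**A null result would still be readable.** True in part. The answers are on file and the split could be reported later, but without pre-specified status.

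**Part of the phone script is not in the public text.** An exclusion there cannot be ruled out, though 5.2, Appendix A and the remaining script all give the any-need rule.

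**Conclusion.** The point holds as a low-cost improvement to the analysis plan, not as a design error. Answers on existing help and wish for help are collected before randomisation for most needs, bear on the primary outcome, and are named in no stated analysis.

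The expected gain from adjustment is about 1.5-4 points of power at the control rate implied by the plan's own effect size, and about 2.5-11 points if control connection among those wanting help is 30-40%. Both ranges assume 20-50% wanting no help, 5-10% of them connecting, and OR 2.1 confined to the rest.

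A reader might infer that adjustment undoes the loss in step 4. It does not: it recovers a small part, and no scenario examined returns to 80%. The firmer benefit is a pre-specified way to interpret the result and to address the trial's question of who needs the more intensive arm.

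**What to change.** Keep eligibility and the all-randomised primary population. In 5.6, before arm results are known:

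1. Reconcile the follow-up triggers with their parent questions (7a with Q6, 15a with Q15). Then derive an indicator for wanting (additional) assistance with at least one identified need, from the b and c items and 9a, with a separate category where the item was not asked.
2. Enter it as a fixed baseline covariate in the primary 8-week connection model.
3. Report its share, add the arm-by-indicator interaction to the modifiers already planned under differences in intervention effectiveness, and report the contrast among those wanting help as a supportive analysis.
4. In the usual-care paragraph, use the index answers on existing assistance, need by need, alongside CPRS.

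Cost: one more model term, a missing category, and repair of the skip logic. No new items are needed, but for Veterans already screened under the present triggers some housing and safety answers may not exist, and these go to the separate category.

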5.3 Informed Consent Procedures

Phase One (Aims 1 and 2): We will not recruit Veterans as subjects for use of secondary data given the minimal risks associated with the study. We will adhere to IRB requirements for informed consent and request a HIPAA waiver of authorization.

Phase One and Two (Aims 1, 2, and 3): The elements of informed consent will be provided in writing and orally, but we will seek a waiver of documentation of informed consent because the recruitment and informed consent process will be conducted entirely by phone, and we believe study poses no more than minimal risk.

To ensure consistent and thorough administration of the informed consent process for this study, the local RAs and investigators will be trained by the PI on the informed consent process and will conduct mock informed consent sessions with the PI prior to performing the informed consent process with patients. Site investigators and RAs will also be trained on the importance of allowing sufficient time for participants to consider the information provided and providing time and opportunity for the participants to ask questions and have those questions answered in order to inform their decision about whether to participate or not. We will conduct periodic internal audits of the informed consent process to ensure informed consent protocols are followed. These audits will take place weekly at the start of the outset of the study (i.e., first month of the trial) and then reduce in frequency as the study continues but will be at least two additional times over the remaining 11 months of the trial.

